10.1.7 Adverse Event and Serious Adverse Event Follow-Up

All AEs and SAEs should be followed until resolution, return to baseline, or until the point it is deemed that further recovery is unlikely. All measures required for AE management and the ultimate outcome of the AE will be recorded in the source document and AE CRF module.

10.1.8 Ongoing Safety Evaluation

A study safety evaluation will be conducted on a regular (monthly) basis by teleconference. Dose exposure, dose-limiting toxicity, AE/SAE profiles and clinical laboratory abnormalities, and other safety measures will be reviewed during each convened meeting. Patient accrual will not be interrupted during the regular scheduled safety evaluations. These discussions will be led by the FPHU Medical Monitor and Principal Investigator.

10.1.9 Clinical Laboratory Tests

Clinical laboratory tests include hematology, coagulation parameters, serum chemistry and urinalysis ([Table 3](#)). Serum pregnancy testing will be performed at Screening for all women of childbearing potential.

Table 3. Clinical Laboratory Parameters

Hematology	Coagulation Parameters	Serum Chemistry	Urinalysis	Bone Marrow Aspirate/Biopsy (Phase 1; Lymphoma Patients only)
Red blood cell count Hemoglobin Hematocrit White blood cell count Differential: Neutrophils ANC Lymphocytes (total counts for all time points; T cell [CD4 and CD8] and B cell counts on Day 1 of each cycle and at EOT) Monocytes Eosinophils Basophils Platelets	Fibrinogen aPTT PT (INR)	Serum creatinine BUN Glucose (non-fasting) Albumin AST ALT LDH Total bilirubin Total protein Alkaline phosphatase Calcium Phosphorus Magnesium Sodium Potassium Chloride Bicarbonate	pH Blood Nitrates Glucose Ketones Leukocytes Protein Microscopic examination	Percent cellularity Lymphocyte subtype Evaluation (eg, positive, negative, indeterminate) Immunohistochemistry Cytometry

Abbreviations: ALT, alanine aminotransferase; aPTT, activated partial thromboplastin time; AST, aspartate aminotransferase; BUN, blood urea nitrogen; EOT, end-of-treatment; INR, international normalized ratio; LDH, lactate dehydrogenase; PT, prothrombin time.

10.1.10 Vital Sign Measurements

Vital sign measurements include temperature, blood pressure and pulse rate. Additional measurements may be obtained if clinically indicated. Any value considered clinically significant by the investigator will be recorded as an AE on the CRF. Clinically significant changes compared to baseline values should be followed until clinical resolution.

10.1.11 Physical Examinations

Complete physical examinations include the following body system evaluations: General Appearance, Skin, Musculoskeletal, Eyes, Ears, Nose, Throat, Cardiovascular, Chest, Abdomen, Lymph Nodes, and Neurological.

Symptom-oriented evaluations will be performed when clinically indicated. Weight will be measured at Screening, Day 1 of each treatment cycle and the End of Treatment Visit.

10.1.12 Electrocardiograms

12-Lead ECGs will be performed at Screening and at End of Treatment.

10.1.13 Tumor Biopsy

A tumor biopsy should be obtained at screening or during Cycle 1 in patients with accessible tissue, if determined to be feasible, in the opinion of the investigator. The biopsy will be used for genetic studies for mutations and other variables to determine tumor molecular subtype which can be important for patients who are candidates for personalized therapy. In addition, laboratory studies using the tumor tissue may be performed.

If the patient's tumor's mutation status has already been characterized these data may be recorded in the clinical database for further analysis.

10.2 Efficacy Assessments

10.2.1 Criteria for Evaluation of Response and Progression

Evaluation of response to treatment and determination of disease progression in patients with solid tumors will be made according to the Response Evaluation Criteria in Solid Tumors (RECIST v. 1.1).¹

10.2.2 Disease Response Criteria

10.2.2.1 Patients with Solid Tumors

- **Evaluation of Target Lesions in Patients with Measurable Disease:**
 - **Complete Response (CR):** Disappearance of all target lesions. Any pathological lymph nodes (whether target or non-target) must have reduction in short axis to < 10 mm.
 - **Partial Response (PR):** At least a 30% decrease in the sum of the diameters of target lesions, taking as reference the baseline sum diameters.
 - **Progressive Disease (PD):** At least a 20% increase in the sum of the diameters of target lesions, taking as reference the smallest sum on study (this includes the baseline sum if that is the smallest on study). In addition to the relative increase of 20%, the sum must also demonstrate an absolute increase of at least 5 mm. (**Note:** the appearance of one or more new lesions is also considered progression).
 - **Stable Disease (SD):** Neither sufficient decrease to qualify for PR nor sufficient increase to qualify for PD, taking as reference the smallest sum diameters while on study.
- **Evaluation of Non-Target Lesions (all other lesions, or in patients with non-measurable disease only)**
 - **Complete Response (CR):** Disappearance of all non-target lesions and normalization of tumor marker level. All lymph nodes must be non-pathological in size (< 10 mm short axis).
 - **Non-CR/Non-PD:** Persistence of one or more non-target lesion(s) and/or maintenance of tumor marker level above the normal limits.
 - **Progressive Disease (PD):** Unequivocal progression of existing non-target lesions, or appearance of one or more new lesions. When the patient also has measurable disease, to achieve 'unequivocal progression' on the basis of non-target disease, there must be an overall level of substantial worsening in non-target disease such that, even in the presence of SD or PR in target disease, the overall tumor burden has increased sufficiently to merit discontinuation of therapy.
- **Time Point Response**

At each protocol-specified time point, an overall response assessment should be made. Criteria for overall response for target and non-target disease are summarized in [Table 4](#) and [Table 5](#).

Table 4. Criteria for Overall Response for Target (+/- Non-target) Disease

Target Lesions	Non-Target Lesions	New Lesions	Overall Response
CR	CR	No	CR
CR	Non-CR/Non PD	No	PR
CR	Not evaluated	No	PR
PR	Non-PD or not all evaluated	No	PR
SD	Non-PD or not all evaluated	No	SD
Not all evaluated	Non-PD	No	NE
PD	Any	Yes or No	PD
Any	PD	Yes or No	PD
Any	Any	Yes	PD

CR = complete response, PR = partial response, SD = stable disease, PD = progressive disease, NE = not evaluable

Table 5. Criteria for Overall Response for Non-target Disease Only

Non-Target Lesions	New Lesions	Overall Response
CR	No	CR
Non-CR/non-PD	No	Non-CR/non-PD
Not all evaluated	No	NE
Unequivocal PD	Yes or No	PD
Any	Yes	PD

CR = complete response, PR = partial response, SD = stable disease, PD = progressive disease, NE = not evaluable

- **Evaluation of Best Overall Response**

The best overall response is the best response recorded across all time points. If CR or PR is recorded, confirmation should be sought 28 days later. When SD is believed to be the best response, no confirmation is required.

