7 STUDY POPULATION

7.1 Inclusion Criteria

Patients must meet all of the following criteria to participate in the study:

- Males and females ≥ 18 years of age
- Patients must meet one of the following criteria:
 - **Cohorts 1 to 10:** Histologically or cytologically confirmed advanced or metastatic solid tumor or lymphoma (lymphoma in Phase 1 only), that is refractory to standard therapy, relapsed after standard therapy, or for which no standard therapy available that is expected to improve survival by at least three months (Cohort 10 in Phase 2a)
 - Or
 - **Cohort 11 (Phase 2a):** Histologically or cytologically confirmed intra- or extra-hepatic cholangiocarcinoma that is refractory to standard therapy, relapsed after standard therapy, or for which no standard therapy available that is expected to improve survival by at least three months
 - Or
 - **Cohort 12 (Phase 2a):** Histologically or cytologically confirmed metastatic and/or unresectable gallbladder carcinoma that has progressed on gemcitabine-based therapy or another systemic therapy and for whom a clinical trial is an appropriate option
 - Or
 - **Cohort 13 (Phase 2a):** Histologically or cytologically confirmed metastatic and/or unresectable urothelial carcinoma that has progressed despite platinum-based therapy. (Note: evidence of progression within 12 months of peri-operative platinum-based therapy will be considered to have met progression criteria.) Patients must also have received a PD-1 or PD-L1 inhibitor and progressed or be ineligible for PD-1/PD-L1 inhibitor therapy or have refused such therapy.
- At least 4 weeks beyond the last chemotherapy (or ≥ 5 half-lives for targeted agents, whichever is shorter), radiotherapy, major surgery or experimental treatment and recovered from all acute toxicities (\leq Grade 1)
- Adequate performance status: Eastern Cooperative Oncology Group (ECOG) ≤ 2 (See [APPENDIX A](#))
- Life expectancy of ≥ 3 months
- Adequate hematologic parameters without ongoing transfusional support:
 - Hemoglobin (Hb) ≥ 9 g/dL
 - Absolute neutrophil count (ANC) $\geq 1.0 \times 10^9$ cells/L
 - Platelets $\geq 100 \times 10^9$ cells/L
- Prothrombin time and activated partial thromboplastin time $< 1.5 \times$ the ULN for the institution. Exceptions are permitted following approval by the Medical Monitor
- Adequate renal and hepatic function:

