11 STATISTICAL METHODOLOGY

11.1 Determination of Sample Size

Phase 1:

The sample size reflects requirements associated with a single patient dose escalation until \geq Grade 2 toxicity is observed, thereafter a 3+3 design. A total of 3 to 54 patients are planned (1 to 6 patients in each of 9 dose cohorts).

Phase 2a:

There are 4 cohorts in Phase 2a. The expansion cohorts will assess the efficacy of FF-10502-01 in a cohort of patients with a variety of solid tumors (Cohort 10), in a cohort of patients with cholangiocarcinoma (Cohort 11), in a cohort of patients with gallbladder carcinoma (Cohort 12), and in a cohort of patients with urothelial carcinoma (Cohort 13).

The primary measure of efficacy in these 4 expansion cohorts will be response according to the RECIST 1.1. criteria. A maximum of 20 patients will be accrued in Cohort 10, a maximum of 50 patients will be accrued in Cohort 11, a maximum of 10 patients will be accrued in Cohort 12, and a maximum of 27 patients will be accrued into Cohort 13.

Cohort 10: Cohort 10 will recruit patients with a variety of solid tumors to explore whether responses are seen in additional tumor types. If the overall response rate amongst these patients is 14%, there will be a less than 5% chance of failing to see a response in at least 1 patient.

Cohort 11 (cholangiocarcinoma): Historically, very low response rates have been observed in cholangiocarcinoma. Cohort 11, with a maximum of 50 patients, has 80% power if the true response rate, p_1 , is 16%, using a 1-sided type I error of 5% with a null hypothesis, p_0 , of 5%. A Simon 2-stage design will be employed so that 50 patients are only recruited if evidence of activity is confirmed at an interim analysis. If after 25 patients have been recruited, there are 1 or fewer responses, enrollment for this cohort may be suspended for futility. If after 50 patients have been recruited, 6 or more responses are observed, the null hypothesis of a 5% response rate will be rejected. An alternative analysis may include all treated cholangiocarcinoma patients—not just those meeting the definition of Cohort 11.

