3.3.1. Primary Endpoints

The primary efficacy endpoint is the proportion of patients in each disease cohort (cholangiocarcinoma, gallbladder carcinoma, urothelial carcinoma, or other solid tumor) with objective response (OR) within 4 cycles of study drug. Thus, this is the proportion of patients in Cohorts 1-12 with an OR within 16 weeks of their first dose of study drug and the proportion of patients in Cohort 13 with an OR within 12 weeks of their first dose of study drug. The OR rate is defined as the proportion of patients with a confirmed complete or partial response. Ninety percent confidence intervals for the OR rate will be estimated. See Appendix A for the schedule of study procedures.

Target Lesions in patients with measurable disease is evaluated by the PI as follows:

- **Complete Response (CR):** Disappearance of all target lesions. Any pathological lymph nodes (whether target or non-target) must have reduction in short axis to < 10mm.
- **Partial Response (PR):** At least a 30% decrease in the sum of the diameters of target lesions, taking as reference the baseline sum diameters.
- **Progressive Disease (PD):** At least a 20% increase in the sum of the diameters of target lesions, taking as reference the smallest sum on study (this includes the baseline sum if that is the smallest on study). In addition to the relative increase of 20%, the sum must also demonstrate an absolute increase of at least 5 mm. (Note: the appearance of one or more new lesions is also considered progression).
- **Stable Disease (SD):** Neither sufficient decrease to qualify for PR nor sufficient increase to qualify for PD, taking as reference the smallest sum diameters while on study.
- **Not Evaluable:** One or more Target Lesions could not be assessed.

Non-Target Lesions (for all other lesions, or in patients with non-measurable disease only) is evaluated by the PI as follows:

- **Complete Response (CR):** Disappearance of all non-target lesions and normalization of tumor marker level. All lymph nodes must be non-pathological in size (< 10 mm short axis).
- **Non-CR/Non-PD:** Persistence of one or more non-target lesion(s) and/or maintenance of tumor marker level above the normal limits.

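### No Phase 2a cohort requires measurable disease, although efficacy is RECIST response; if patients without it enter the denominator, the stated 80% power may be diluted, and the SAP's response table has no clear row for them

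*Protocol*

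**What the plan says.** Eligibility (Protocol 7.1, 7.2 and synopsis) is set by histology, prior therapy, performance status, laboratory values and similar items. For Cohort 11 the disease criterion begins "Histologically or cytologically confirmed intra- or extra-hepatic cholangiocarcinoma that is refractory to standard therapy, relapsed after standard therapy". Neither the inclusion nor the exclusion criteria of any cohort mention a measurable lesion.

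The endpoint is tumour response. Protocol 11.1 states: "The primary measure of efficacy in these 4 expansion cohorts will be response according to the RECIST 1.1. criteria". Protocol 11.3.2.1 defines the rate as confirmed complete or partial response (CR or PR) among the full analysis set (FAS). Protocol 11.2 and SAP 2.2.1 build the FAS from patients with a valid baseline and at least one later assessment, with no measurable-disease condition.

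Protocol 10.2.2.1 has a block headed "Evaluation of Non-Target Lesions (all other lesions, or in patients with non-measurable disease only" and a separate scoring table, "Table 5. Criteria for Overall Response for Non-target Disease Only". Its outcomes are CR, Non-CR/non-PD, NE and PD. SAP 3.3.1 repeats the provision ("Non-Target Lesions (for all other lesions, or in patients with non-measurable disease only) is evaluated by the PI as follows"), but its overall-response table reproduces only the target-lesion version.

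The decision counts are in Protocol 11.1. For Cohort 11: "Cohort 11, with a maximum of 50 patients, has 80% power if the true response rate" is 16%, "using a 1-sided type I error of 5% with a null hypothesis" rate of 5%. At the interim, "If after 25 patients have been recruited, there are 1 or fewer responses, enrollment for this cohort may be suspended for futility". Six or more responses in 50 reject the null. Cohort 13 stops at 0 of 15 and rejects at 4 or more of 27, with rates of 5% and 20%.

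**The concern.** PR is defined by the sum of target-lesion diameters. A patient with no target lesion cannot reach PR, and responds only if all non-target disease disappears and tumour markers normalise. Such a patient takes one of a fixed number of places with a reduced chance of response.

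The same patient is also missing from the second Cohort 11 continuation criterion, stable disease in at least 30% after 25 patients (Protocol 11.1), because Table 5 offers Non-CR/non-PD and not SD. At stake is a missed signal: an active drug is more likely to meet the futility count or fall short of the final count.

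Separately, the SAP leaves the programmer to invent a rule for the primary efficacy endpoint in these patients.

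**Working it through.** **Inputs.** From Protocol 11.1:
- Cohort 11: n1 = 25, stop at r1 = 1 or fewer; n = 50, reject at r = 6 or more; p0 = 5%, p1 = 16%.
- Cohort 13: n1 = 15, stop at r1 = 0; n = 27, reject at r = 4 or more; p0 = 5%, p1 = 20%.

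Not in the documents, so assumed: the share m of patients with non-measurable disease only (2% to 20%), and their CR rate c (0%, then 5%). It is also assumed that p1 applies to patients with measurable disease.

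**Formula.** Response probability per enrolled patient: q = p1(1 − m) + c·m. Power with the futility rule binding: the sum over x = r1+1 to n1 of P[Bin(n1, q) = x] × P[Bin(n − n1, q) ≥ r − x].

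**Step 1: reproduce the plan (m = 0).** Cohort 11: power 80.7%, attained type I error 3.5%. Cohort 13: power 81.0%, type I error 4.3%. Both agree with the stated 80% and 5%.

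**Step 2: dilution with c = 0.**

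| m | Cohort 11 q | Power, binding | Power, non-binding | Cohort 13 q | Power, binding | Power, non-binding |
|---|---|---|---|---|---|---|
| 0% | 16.0% | 80.7% | 83.2% | 20.0% | 81.0% | 81.8% |
| 2% | 15.68% | 79.1% | 81.7% | 19.6% | 79.7% | 80.4% |
| 5% | 15.2% | 76.5% | 79.2% | 19.0% | 77.5% | 78.2% |
| 10% | 14.4% | 71.7% | 74.5% | 18.0% | 73.4% | 74.2% |
| 20% | 12.8% | 60.3% | 63.1% | 16.0% | 63.9% | 64.7% |

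**Step 3: chance of meeting the futility count.** Cohort 11: (1 − q)^25 + 25q(1 − q)^24 = 7.4% at m = 0, 10.7% at 10%, 15.2% at 20%. Cohort 13: (1 − q)^15 = 3.5%, 5.1% and 7.3%.

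**Step 4: allow complete responses, c = 5%.** At m = 10%, q = 0.144 + 0.005 = 14.9% in Cohort 11 (power 74.8%) and 0.18 + 0.005 = 18.5% in Cohort 13 (75.5%). At m = 20%, q = 13.8% and 17.0%, with power 67.7% and 68.9%.

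**Step 5: drop these patients without replacing them.** At m = 10% with unchanged cut-offs, about 45 evaluable (22 at the interim) gives 71.7% in Cohort 11, and about 24 evaluable (14 at the interim) gives 73.1% in Cohort 13. Exclusion alone does not restore power.

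**Step 6: type I error.** If the 5% null is diluted in the same way, type I error at m = 10% falls to 2.2% (Cohort 11) and 3.1% (Cohort 13).

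**Step 7: Cohorts 10 and 12.** The plan's chance of seeing no response is 0.86^20 = 4.9% and 0.74^10 = 4.9%, matching its claim of below 5%. At m = 10%: (1 − 0.126)^20 = 6.8% and (1 − 0.234)^10 = 7.0%.

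**Step 8: the SAP table.** A patient with no target lesions is caught by the PD rows if there is non-target PD or a new lesion. Otherwise every CR, PR and SD row needs a target-lesion result, and the NE row describes target lesions not all evaluated, which is a different situation. Protocol Table 5 would give CR or Non-CR/non-PD; the SAP table gives no clear answer.

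**The case against.** Several points on the other side stand.

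- **The share is unknown.** At 2% the loss is under two percentage points. The populations are advanced, and the design summary asks for documented progression after previous therapy. This does not guarantee a measurable lesion, but nothing in the documents supports a share of 10% or 20%.
- **A reader might infer that the protocol expects such patients in Cohorts 11 and 13.** It does not say so. Section 10.2.2.1 is a general scoring section that also serves the mixed-tumour Phase 1 cohorts.
- **A reader might infer that the response rate is biased downward as a matter of fact.** That needs p1 to be a rate for measurable disease. Protocol 11.1 does not say which population p1 describes; if it is the population as enrolled, the dilution is already included.
- **Entry to the denominator is not certain.** The Protocol 11.2 wording makes the FAS specific to each measure, and whether a patient without target lesions has a valid response baseline is not defined. Table 5 suggests yes. If not, Step 5 shows a similar loss from the smaller number evaluable.
- **Meeting the futility count is not stopping.** Enrolment may be suspended, recruitment does not pause, and prolonged stable disease is weighed first.
- **Response is a secondary objective.** The primary objective is safety, MTD, DLT and RP2D. SAP 2.4.2 and 2.4.6 plan no formal hypothesis tests and no formal interim analysis. The counts in Protocol 11.1 nevertheless govern enrolment and the conclusion on activity.

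None of this removes the two textual facts: no measurable-disease criterion, and no SAP rule for patients without target lesions.

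**Conclusion.** The point holds as a conditional one. The missing entry criterion, the absence of PR and SD in Table 5, and the gap in the SAP table are plain on the text. The power loss rests on three assumptions: p1 refers to patients with measurable disease, patients without it are in the FAS, and their share is not negligible. On those terms the loss runs from under two points at a 2% share to about 20 points in Cohort 11 and 17 in Cohort 13 at a 20% share with no responses; a 5% CR rate softens it.

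The direction is conservative: an active drug may be missed, and a false claim of activity becomes less likely. It would go too far to say that the trial is underpowered or that this must be repaired before it can meet its primary objective. It should be fixed, because the improvement is cheap.

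**What to change.** 1. In Protocol 7.1 and the synopsis, for patients still to be enrolled in Cohorts 11 and 13, and preferably 10 and 12, add: at least one measurable target lesion by RECIST v1.1 on the screening CT/MRI.
2. Carry Protocol Table 5 into SAP 3.3.1, and state whether Non-CR/non-PD counts toward the Cohort 11 stable-disease criterion.
3. For patients already enrolled without a measurable lesion, including Phase 1 MTD patients counted toward Phase 2a, keep them in the FAS rate as non-responders unless they reach CR. Also report the rate in patients with measurable disease at baseline.
4. State in advance which of the two rates is used for the 25/50 and 15/27 decision counts. If it is the measurable-disease rate, enrol until that set reaches 50 and 27; otherwise the loss in Step 5 remains.

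The cost is one inclusion line by amendment and a short SAP addition. The screening scan is already required (Protocol 9.1) and a screening target-lesion listing is already planned (SAP 4.3), so no new procedure is needed. The downside is that a few patients with only non-measurable disease could no longer enrol.

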10.2.3 Efficacy Endpoints

10.2.3.1 Primary Efficacy Endpoint

The primary efficacy endpoint is the proportion of patients with objective response achieved by Week 16 (Cohorts 1 to 12) or Week 12 (Cohort 13) following FF-10502-01 treatment.

- **Patients with Solid Tumors**

Objective responses for patients with solid tumors include a best response of complete response (CR) or partial response (PR), as defined above.

10.2.3.2 Secondary Efficacy Endpoints

Duration of Response: length of time from the date of first evidence of response (CR or PR) to date of first evidence of PD

Duration of SD: length of time from the date of the first administration of study drug to the date of first evidence of PD

Progression-Free Survival: length of time from the date of first administration of study drug to the first objective evidence of disease progression or death, whichever is earlier

Overall Survival: length of time from the date of first administration of study drug to the date of death from any cause

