Statistical methods: Safety Endpoint Analyses: 
Safety endpoints for AEs include the following: incidences of all treatment-emergent adverse events (TEAEs) and all serious adverse events (SAEs); number and incidence of TEAEs and SAEs by severity; number and incidence of TEAEs and SAEs by relationship to study drug; number and incidence of all Grade 3 and 4 TEAEs and by severity and relationship to study drug; and discontinuation of patients from the study due to AEs or death. Safety endpoints for AEs, clinical laboratory tests, vital signs, ECG, and physical examination findings will be specified in the statistical analysis plan. Physical examination findings and ECGs will be listed. All other safety data will be summarized using descriptive statistics.
 Efficacy Endpoint Analyses: 
Response rates will be summarized using number and percentage of patients with a best response of CR, PR, SD or PD assessed by RECIST v 1.1 across all time points. For duration of response, duration of stable disease, PFS and OS, the Kaplan-Meier product-limit method will be used to estimate the median survival. Patients who do not have disease progression will be censored at the time of last contact.
 
Progression-free survival will be calculated from the date of first treatment to the date of progression or death.
 
Overall survival will be calculated from the date of first treatment to the date of death from any cause; patients who do not experience death will be censored at the time of last contact.
 
SAS Version 9.4 or higher for Windows (SAS Institute, Cary, NC) or higher will be used for all analyses.
 Pharmacokinetic and Pharmacodynamic Endpoint Analyses: Analysis plans will be described in the written plans provided by the laboratories performing the analyses.	

CONTENTS

2	SYNOPSIS	3
3	LIST OF ABBREVIATIONS.....	14
4	INTRODUCTION	17
4.1	FF-10502-01 Background	17
	Figure 1. Chemical Structure of FF-10502-01	18
4.2	ZK 820973 Preclinical Summary	18
4.2.1	ZK 820973 Preclinical Pharmacokinetics, Distribution, Metabolism, Excretion	18
4.2.2	ZK 820973 Preclinical Safety Pharmacology.....	19
4.2.3	ZK 820973 Genetic Toxicology	19
4.3	FF-10502-01 Preclinical Studies	19
4.3.1	FF-10502-01 In Vitro Anti-tumor Activity	19
	Table 1. Growth Inhibition of FF-10502-01 and Gemcitabine in Human Tumor Cell Lines ..	20
4.3.2	FF-10502-01 In Vivo Anti-tumor Activity.....	20

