11.3.2.2 Secondary Efficacy Endpoints

Duration of response, duration of SD, PFS and OS curves will be estimated by disease cohort using Kaplan-Meier product limit estimates. Median and 90% confidence interval of time-to-event will be estimated. Progression-free survival will be calculated from the date of first dose of study drug to the date of first documented evidence of disease progression or death, whichever is earlier. Overall survival will be calculated from the date of first dose of study drug to the date of death due to any cause. Patients who did not experience progression or death will be censored at the time of last contact.

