3.3.2. Secondary Endpoints

Duration of Objective Response: length of time from the date of first evidence of response (CR or PR) to date of first evidence of PD or death. Patients who did not experience progression or death will be censored at the time of last contact (on the long-term follow-up date or the end of study date, whichever is later).

Duration of Stable Disease: length of time from the date of first evidence of response (CR, PR or SD) to date of first evidence of PD or death. Patients who did not experience progression or death will be censored at the time of last contact (on the long-term follow-up date or the end of study date, whichever is later).

Progression-Free Survival: length of time from the date of first administration of study drug to the date of first evidence of disease progression or death. Patients who did not experience progression or death will be censored at the time of last contact (on the long-term follow-up date or the end of study date, whichever is later).

Overall Survival: length of time from the date of first administration of study drug to the date of death from any cause. Patients who did not experience death will be censored at time of last contact (on the long-term follow-up date or the end of study date, whichever is later).

Duration of response, duration of stable disease, progression-free survival, and overall survival will be estimated using Kaplan-Meier product limit estimates and the estimated median and 90% confidence interval of the time-to-event.

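### The protocol's definitions end duration of response and duration of SD at PD only, the SAP ends them at PD or death, and the synopsis censors deaths without progression that the SAP counts as events

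*Protocol*

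**What the plan says.** **End event.** Protocol 10.2.3.2 defines duration of response as "length of time from the date of first evidence of response (CR or PR) to date of first evidence of PD". Duration of SD in the same list also stops at first evidence of PD. The next item, PFS, runs to "the first objective evidence of disease progression or death, whichever is earlier", so the list names death for PFS and omits it for both durations. SAP 3.3.2 defines duration of response as "length of time from the date of first evidence of response (CR or PR) to date of first evidence of PD or death" and ends duration of SD at PD or death as well.

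**Censoring.** The synopsis, under Efficacy Endpoint Analyses, lists duration of response, duration of SD, PFS and OS as Kaplan-Meier endpoints and then states: "Patients who do not have disease progression will be censored at the time of last contact". Only OS has a separate censoring rule there. Protocol 11.3.2.2, covering the same four endpoints, states: "Patients who did not experience progression or death will be censored at the time of last contact". SAP 3.3.2 applies the section 11.3.2.2 rule to duration of response, duration of SD and PFS.

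**Start of duration of SD.** Protocol 10.2.3.2 counts from the first administration of study drug. SAP 3.3.2 counts from the first assessment that shows CR, PR or SD.

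**Reporting.** Protocol 11.3.2.2 reports these endpoints by disease cohort: "Median and 90% confidence interval of time-to-event will be estimated".

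**The concern.** A patient who dies cannot progress later. Censoring that death in a Kaplan-Meier estimate assumes the patient had the same future risk of PD as those still alive and in response, so an unfavourable outcome drops out of the event count and the curve is pushed upward.

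Death before a scan documents PD is plausible here. Most cohorts require refractory or relapsed disease, ECOG status may be as high as 2, and required life expectancy is only 3 months or more. Scheduled imaging is every 8 weeks in Cohorts 1 to 12 and every 6 weeks in Cohort 13.

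At stake is whether the reported median duration of response and median duration of SD each have one meaning. With two definitions in current text, the choice could be made after the data are seen, and one option cannot give the shorter median.

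**Working it through.** The documents state no expected median, event count or precision for these endpoints, so there is no plan figure to reproduce. The check is a comparison of the rules, followed by an illustration of size.

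**1. A responder who dies without documented PD**

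| Text applied to duration of response | Treatment of the death |
|---|---|
| Protocol 10.2.3.2 with the synopsis | Censored at last contact |
| Protocol 10.2.3.2 with protocol 11.3.2.2 | Not a defined end event, and not in the group to be censored |
| SAP 3.3.2 | Event |

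The end-event conflict and the treatment of the death are the same for duration of SD.

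**2. Direction.** The Kaplan-Meier curve is a product of factors (1 − 1/number at risk), one per event time. Relabelling a death as censored replaces its factor by 1 and leaves every later risk set unchanged. The death-censored curve is therefore at or above the other at every time, and its median is never shorter.

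**3. Size under constant hazards.** Let λ be the total hazard of PD or death, and s the share of first events that are deaths without PD.

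- Deaths as events: median = ln 2 / λ.
- Deaths censored: median = ln 2 / (λ(1 − s)).
- Ratio = 1 / (1 − s).

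Both s and the 4-month median below are assumptions.

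| s | Ratio | A 4.0-month median becomes |
|---|---|---|
| 10% | 1/0.90 = 1.11 | 4.4 months |
| 15% | 1/0.85 = 1.18 | 4.7 months |
| 20% | 1/0.80 = 1.25 | 5.0 months |
| 25% | 1/0.75 = 1.33 | 5.3 months |

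**4. Size against sampling error.** In Cohort 11 the 16% alternative gives 0.16 × 50 = 8 responders. In simulated cohorts of 8 (exponential times, median 4 months, s = 20%), the Kaplan-Meier median had a standard deviation of 1.86 months. The 1.0-month shift is then 1.0/1.86 = 0.54 standard errors. The death-censored median was longer in about 59% of cohorts, identical in about 41%, and shorter in none.

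**5. Small example.** Take 8 responders with assumed times of 2, 3, 4, 5, 6, 8, 10 and 12 months, and the median as the first time the curve is at or below 0.5.

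- All are events: after month 5 the curve is 4/8 = 0.50, so the median is 5 months.
- Month 3 is a censored death: 7/8 × 5/6 × 4/5 = 0.583 at month 5, then × 3/4 = 0.438 at month 6. The median is 6 months.
- Months 3 and 5 are censored deaths: 7/8 × 5/6 × 3/4 = 0.547 at month 6, then × 2/3 = 0.365 at month 8. The median is 8 months.

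**6. Start date for duration of SD.** If SD is first shown at the first scheduled scan, the SAP clock starts about 8 weeks (1.8 months) after the protocol clock in Cohorts 1 to 12, and about 6 weeks (1.4 months) after it in Cohort 13. Both gaps exceed the 1.0-month shift at s = 20% in step 3. They act in the same direction, since the protocol version is again the longer one.

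**The case against.** The strongest reply is that the sound rule is already written where the analysis is specified. SAP 3.3.2 is explicit, and the censoring rule in protocol 11.3.2.2 agrees with it. The censored reading needs section 10.2.3.2 combined with one synopsis sentence, against the protocol's own methods section. That stands, and it means the protocol is also inconsistent with itself; this is not a clean split between protocol and SAP. It does not remove the end event in 10.2.3.2, which omits death while the PFS item beside it includes it.

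A reader might infer that PFS deaths are censored too, because the synopsis sentence follows a list that includes PFS. The documents do not support this. The next synopsis sentence says "Progression-free survival will be calculated from the date of first treatment to the date of progression or death", and protocol 10.2.3.2, protocol 11.3.2.2 and SAP 3.3.2 all count death. Applied literally to every listed endpoint, the sentence would also censor OS deaths in patients without progression, which the synopsis's own OS rule excludes. For PFS it is loose wording, not a competing definition.

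Two further replies have some force. Protocol 10.2.4 allows scans at other times at the investigator's discretion, and section 9.3 schedules one at relapse or progression; both could reduce deaths without documented PD. And with about 8 responders, the illustrated shift lies within sampling error. Neither makes the two definitions equivalent.

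**Conclusion.** The point holds for duration of response and duration of SD. A death without documented PD is censored under the synopsis with protocol 10.2.3.2, and is an event under SAP 3.3.2. Censoring gives a median that is never shorter and usually longer, by a factor of 1.11 to 1.33 if hazards are constant and 10% to 25% of events are such deaths. It would be too strong to say that the protocol version of median duration of response is always longer, since with few responders the two medians often coincide.

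The consequence is moderate. These are secondary, descriptive endpoints. The primary response rate and the Simon rules for Cohorts 11 and 13 use response counts, and the stable-disease consideration at the interim uses a proportion or number of patients, so none depends on these medians. For duration of SD, the unmatched start date may matter more than the end event. The wording should be reconciled before analysis.

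**What to change.** 1. In protocol 10.2.3.2, end both duration of response and duration of SD at the earlier of first documented PD and death from any cause, as the SAP already does.
2. In the synopsis, restrict the censoring sentence to patients who have neither progressed nor died. This brings it into line with protocol 11.3.2.2 and SAP 3.3.2, and removes the loose wording on PFS.
3. In the same edit, choose one start date for duration of SD and use it in protocol 10.2.3.2 and SAP 3.3.2. Aligning only the end event would still leave two different medians.

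The cost is a few sentences across the two documents, with no new data collection and no change to sample size. The reported medians may be slightly shorter than under the PD-only wording.
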